
Study Design

This clinical study will involve 26 human subjects pre-screened at Columbia University with the presence of at least one implant presenting with early to moderate peri-implantitis. Peri-implantitis has been defined as an implant restoration with inflamed bleeding gingiva, probing depths around the implant of 5- 8mm, bone loss and exposure of threads around the implant (limited to one-third of the threads exposed). The purpose of this study is to determine the benefits of treating peri-implantitis with a closed laser approach known as the "Repair Protocol" using an Er,Cr:YSGG laser compared with traditional non-surgical therapy. Each subject, when determined to fall under the parameters of the study for peri-implantitis, will be randomly assigned to one of two groups: the test Er,Cr:YSGG laser group or the control group. The study will constitute a human double-blind randomized clinical trial in which both examiners and patients will be blinded to the treatment. In order to ensure the blinding of the patients, the laser will be applied to all implants, although it will not be activated in the control group. The therapist will be the same person throughout the study while the examiners will be calibrated. The two groups that will constitute the study and the procedures that will be applied are:

Experimental: Scaling and root planning with an ultrasonic or piezoelectric instrument and hand instrumentation with hand instruments. No prosthetic components will be removed. Application of laser therapy following the specifics of the company.

Control: Scaling and root planning with an ultrasonic or piezoelectric instrument and hand instrumentation with hand instruments. A sham, inactivated laser, treatment will be delivered.

Data to be collected include: Primary outcome measures will include: presence of bleeding on probing, probing depth, and the progression of bone loss around the implant, as measured with bone sounding under local anesthesia and radiographically with the aid of a stent. Secondary outcome measures will include: Gingival index (GI), Plaque Index, mobility, and suppuration.

Statistical Procedures

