Dental implants are becoming more and more popular as a means to replace missing teeth. As more dental implants are being placed each year, clinicians are facing the challenges of common causes for failure or compromise of these dental implants. Gum disease, which has plagued natural teeth for many years, can manifest on dental implants in the form of a disease known as peri-implantitis. Peri-implantitis occurs when the presence of bacteria leads to inflammation of the area, and can be the reason for loss of bone around implants. Currently, there is no standard method for treating peri-implantitis. There are several common methods for treating this disease. One method involves cleaning off the implant with scalers in a manner similar to teeth during cleanings. The other method utilizes the same method and adds the use of a laser to remove most of the bacteria from the surface of the implant. In this study, we would like to compare these two methods and see if there is any additional benefit from using the laser technology. The goal is to determine which method is more effective at arresting the progression of peri-implantitis. For this means, we will be taking clinical measurements and X-rays. This will allow us to determine the status of the implant, improvement in the inflammation and changes in bone level. The implants will be treated at the baseline and checked during the follow-up appointments with the last appointment provided at the 9 months.

Risks, Benefits, Alternatives

The risk involved with the laser debridement directly to the patient is minimal. Potential risks may be postoperative infection or soft tissue trauma. The procedure is a conservative surgery-free debridement of the implant with the Biolase laser, and there is very little risk of having postoperative complications. Proper protocol for laser safety will be followed when utilizing the Biolase laser. Both procedures involved with the study are the standard of care for treatment.

Risks and complications of the use of lasers involve: eye and skin damage, thermal damage of the tissues and the adjacent structures, alterations of the implant, restorations of other surfaces, damage of critical structures (i.e. nerves and vessels), embolism, water splashing and rupture of the tip of the laser.

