The benefits of the study with enrolled patients is that they are able to receive treatment on ailing implants, whether through non-surgical means or with use of the laser. There is no compensation for the study, since it utilizes therapy that the patient would have needed regardless of participation. Currently, because no standardized protocol exists for the treatment of peri-implantitis, the benefit of this study will be to help collect data on treatment methods to gain additional knowledge on the most optimal treatment methods for peri-implantitis. This is an area that has very little conclusive evidence in terms of treatment modalities that are most effective, and more information is needed to determine the most effective way to treat peri-implantitis.

The alternative intervention for the subject is to not participate in the study and have the implant treated outside the study.

Data and Safety Monitoring

The data will be recorded on paper when the patient is seen by the operator. The study data will then be stored in an Excel file on an encrypted desktop or laptop computer immediately after the encounter with the patient. The paper documents used to collect data will then be destroyed once recorded electronically. There is minimal risk, and therefore there will be no data and safety monitoring board involved. The measurements will also be recorded in the electronic database for every patient (Axium) as a part of their dental treatment records.

The readings for gingival bleeding, periodontal probing, and attachment loss will be monitored for each patient at every visit and compared with previous readings for every patient. Monitoring for any unexpected outcomes, such as a severe increase in attachment loss/probing or gingival inflammation, will be completed after every visit with a patient for study purposes. Any patient showing aberrant findings and potential high risk for the study treatment will be identified and reported to the IRB. All investigators will be tasked with the data and safety monitoring for all patients.

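### The listed laser harms have no systematic record or by-arm table, and the safety readings due at every visit conflict with the no-probe recall visits

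*Combined protocol and SAP*

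**What the plan says.** **Harms named.** Risks, Benefits, Alternatives gives infection after the procedure and soft tissue trauma as potential risks. It then lists complications of laser use: "eye and skin damage, thermal damage of the tissues and the adjacent structures, alterations of the implant", followed by restorations and other surfaces, nerve and vessel injury, embolism, water splash and breakage of the tip. The same section rates the risk as minimal.

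**Harms monitored.** In Data and Safety Monitoring, "The readings for gingival bleeding, periodontal probing, and attachment loss will be monitored for each patient at every visit", and these are "compared with previous readings for every patient". A second provision, "Monitoring for any unexpected outcomes, such as a severe increase in attachment loss/probing or gingival inflammation", is to be carried out after each visit. Escalation is by one sentence: "Any patient showing aberrant findings and potential high risk for the study treatment will be identified and reported to the IRB". On oversight: "There is minimal risk, and therefore there will be no data and safety monitoring board involved".

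**Outcomes.** Study Design gives bleeding on probing, probing depth and bone loss as primary. Then: "Secondary outcome measures will include: Gingival index (GI), Plaque Index, mobility, and suppuration". The Scientific Abstract has a slightly different primary list, with gingival index and without probing depth. Neither list contains an adverse event or a device event.

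**Visits.** Study Procedures has patients return at 1 week and at 3, 6 and 9 months. It schedules probing depth, bleeding on probing, attachment level and recession at the initial and 9-month visits, and limits recall visits to supragingival polishing with no probe.

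**The concern.** Only the test arm receives active laser energy and the Repair Protocol steps, which include de-epithelialization, gingivectomy where needed and bone decortication. The Medical Device section gives the phase as feasibility, and the hypothesis section calls the trial a pilot. Describing harms is a natural product of such a study. The sham control, with patients and examiners blinded, would allow a fair description by arm.

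The plan does not use that opportunity. Run as written, the trial would end without a by-arm record of most of the harms it names. In addition, the probing and attachment readings that the safety section relies on are not scheduled at three of the four follow-up visits.

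**Working it through.** **1. Listed harms against what is collected.** The list is from Risks, Benefits, Alternatives. The collected items are from Study Design, Study Procedures and Data and Safety Monitoring.

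| Listed harm | Nearest collected item |
|---|---|
| Postoperative infection | Suppuration, gingival index (indirect) |
| Soft tissue trauma | Recession, gingival index (indirect) |
| Thermal damage of tissue or adjacent structures | Recession, bone level, mobility (partial, indirect) |
| Eye or skin injury | None |
| Nerve or vessel injury | None |
| Embolism | None |
| Alteration of implant or restoration | None |
| Water splash, tip breakage | None |

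Bleeding, probing and attachment readings would not detect the last five rows. The unexpected-outcomes provision could catch some of those harms, but it comes with no form, definition, grading or tabulation.

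**2. Type of comparison.** The safety readings are compared with the same patient's earlier values. No section plans a comparison or table of harms by arm.

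**3. Visits.** Data and Safety Monitoring counts on readings at each visit. Study Procedures provides probing and attachment readings at the initial visit and at 9 months only, and no probe at recall. Read literally, both cannot hold at 1 week, 3 months and 6 months.

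**4. What complete recording could show.** The only input is n = 13 laser patients, from Statistical Procedures. That figure rests on a 1.72 mm difference, SD 1.13 mm, 90% power and alpha 0.05. The sidedness is not stated, so two-sided is assumed.

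- Normal formula: n = 2 × [1.13 × (1.960 + 1.282) / 1.72]² = 9.07, so 10 per arm.
- Two-sample t-test: 10.13, so 11 per arm.

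The stated 13 is therefore more than these inputs require. This does not affect the present point, and 13 is used below.

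Zero events in 13:
- one-sided 95% upper bound: 1 − 0.05^(1/13) = 20.6%
- two-sided exact 95% upper limit: 1 − 0.025^(1/13) = 24.7%

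Chance of at least one event in the laser arm, 1 − (1 − p)^13. The rates p are assumptions, since the documents give none:

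| True rate p | Chance of at least one event |
|---|---|
| 1% | 12% |
| 2% | 23% |
| 5% | 49% |
| 10% | 75% |
| 20% | 94.5% |

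**5. Whether to test.** Two-sided Fisher's exact test, 13 per arm:
- 4 against 0 events: 2 × C(13,4)/C(26,4) = 2 × 715/14,950 = 0.096
- 5 against 0 events: 2 × C(13,5)/C(26,5) = 2 × 1,287/65,780 = 0.039

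So at least five events against none are needed for p < 0.05. Power is about 8% at assumed rates of 20% against 2%, and 28% at 30% against 2%. A significance test on harms would tell the reader almost nothing.

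**The case against.** The strongest reply is that the safety wording is open. The examples given for unexpected outcomes are only examples, and the IRB sentence is not limited to periodontal findings. An eye or nerve injury after a procedure described as minimal risk would naturally count as both unexpected and aberrant. This stands. A reader might infer that the listed harms are expected ones and so fall outside the rule, or that a serious injury could not reach the IRB. The documents support neither: they speak of potential risks and of complications, and listing a risk beforehand does not make it expected in a given patient.

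A reader might also infer that nothing is checked at 1 week. That goes too far, because monitoring for unexpected outcomes follows every visit and 1 week is a scheduled visit. The monitoring is unstructured, but it exists.

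It is also fair to say that some outcomes bear on harm. Suppuration, gingival index, mobility, recession and bone level may partly reflect infection, tissue trauma or bone damage, so it would be wrong to say that no listed harm leaves any trace in the data.

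Finally, 26 patients are few, and the protocol describes both treatments as standard of care. That argues against elaborate safety machinery and against a test. It does not argue against a short record of harms the protocol itself names. Case-by-case reporting at the investigators' discretion yields no count by arm.

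**Conclusion.** The point holds as a gap in systematic collection and reporting. No section provides for a structured record or a by-arm table of the listed harms. Eye or skin injury, nerve or vessel damage, embolism, alteration of the implant or restoration, water splash and tip breakage have no counterpart among the collected outcomes. Separately, the every-visit readings in Data and Safety Monitoring and the no-probe recall visits in Study Procedures contradict each other and must be reconciled.

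It is tempting to add that the omission is what stops the trial from supporting its statement of very little risk. That does not follow. With complete recording and no events in 13 laser patients, true rates up to about 21% (one-sided) or 25% (two-sided exact) would remain possible. The gain from recording is description: a harm with an assumed true rate of 10% has about a 75% chance of appearing at least once in the laser arm.

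These figures assume 13 treated and fully followed laser patients. The finding of a gap rests on the text alone. It is a worthwhile and cheap improvement, not a fatal flaw.

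**What to change.** 1. In Data and Safety Monitoring, have the therapist record procedure and device events on the treatment day: tip breakage, water splash and any immediate injury. Study Design names only examiners and patients as blinded, and the therapist has to know whether the laser is active, so this costs no blinding.
2. At the existing 1-week and 3-, 6- and 9-month visits, record patient-reported or visible harms: infection, soft tissue or thermal injury, nerve symptoms, eye or skin injury, and visible damage to the restoration. Use the same neutrally worded form in both arms so that it does not reveal allocation. It needs no probe. Changes to the implant surface cannot readily be seen with a closed technique and no prosthesis removal, so the form should ask only for what is visible.
3. Add adverse events by arm as a descriptive secondary outcome, with exact confidence intervals and no significance test.
4. State that the IRB reporting sentence also covers the harms listed in Risks, Benefits, Alternatives.
5. Reconcile Data and Safety Monitoring with Study Procedures on which readings are taken at which visits.

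The cost is a short form, a few minutes per visit and one table. Sample size, visit schedule, procedures and staffing need not change for items 1 to 4.
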